University of Sao Paulo

**DEVELOPMENT OF A MOBILE APPLICATION TO PROMOTE SELF-CARE IN PATIENTS
WITH FIBROMYALGIA**

[name]

[name]

The study protocol was registered at ClinicalTrials.gov.

Registration No.: NCT0300491

Sao Paulo

July 14th 2014

Objectives

The purpose of this work was to develop a mobile application software for the promotion of self-care and assess the effectiveness of its use during six weeks on health-related quality of life, symptoms and self-care agency of patients with FMS, and to compare the results to the use of a paper book of similar content. Secondarily, patients' adherence to ProFibro app was evaluated.

Methods

A randomized, single-blind, controlled trial was conducted in the Physical Therapy Clinical Research and Electromyography Laboratory at the Physical Therapy, Speech Therapy and Occupational Therapy Department of the School of Medicine of the University of São Paulo (USP), in the city of São Paulo, Brazil. The project was approved by the Research Ethics Committee of the School of Medicine, University of São Paulo (No. 274/14).

Participants (eligibility criteria)

Volunteers were identified using the USP Newspaper and related social media. After answering a screening questionnaire sent by email, potential participants were invited to a face-to-face assessment to confirm eligibility. All participants signed a written informed consent prior to entering the study.

The study included adults and middle-aged individuals (19-59 years) diagnosed with FMS, according to the 2010 American College of Rheumatology (ACR) diagnostic criteria¹, who were smartphone users and completed elementary education. Exclusion criteria were: individuals undergoing physical therapy or treated in the last three months; diagnosis of other conditions causing chronic pain (neuropathies, rheumatoid arthritis, osteoarthritis, spinal stenosis or cancer); severe mental disorders (schizophrenia, psychosis, bipolar affective disorder, severe depression); hearing or visual impairment.

Sample Size

The sample size was calculated to detect the minimal clinically important difference (MCID) of 14% between two groups in health-related quality of life, measured by the FIQR, with a standard

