deviation of 24.3.^{2, 3} Calculations indicated that a sample size of 30 participants would provide a power of 80% at a level of significance of 5%. Five participants were added to each group to compensate for possible dropouts, resulting in a total of 40 participants.

Randomization

Participants were randomly allocated into Experimental and Control Groups. A physical therapist who was not involved in the trial concealed a computer-generated random sequence in sequentially numbered, opaque, sealed envelopes.

Outcomes

An outcome assessor blinded to the interventions enrolled participants in the trial and evaluated them at baseline and after six weeks of intervention.

At baseline, the following demographic and clinical data were collected: age, sex, marital status, level of education, family income, duration of the syndrome and use of medication.

The primary outcome was health-related quality of life measured by the Brazilian Portuguese version of the FIQR.^{3, 4} The FIQR has 21 questions based on an 11-point numeric rating scale of 0 to 10, with 10 being 'worst'. All questions are framed in the context of the past seven days. The FIQR is divided into three domains: (a) Function (contains nine questions), Overall Impact (contains two questions), and (c) Symptoms (contains ten questions regarding pain, stiffness, lack of restorative sleep, poor energy, anxiety, depression, tenderness, memory, balance and environmental sensitivity). The Function score is the sum of the nine questions divided by 3 (range 0 to 30), the Overall Impact score is the sum of two questions (range 0 to 20), and the Symptoms score is the sum of the ten questions divided by 2 (range 0 to 50). The total FIQR is the sum of the three domain scores (range 0 to 100).

Secondary outcomes were: pain measured by the Widespread Pain Index (WPI)¹ and the Visual Analog Scale (VAS)⁵; severity of symptoms measured by the Symptom Severity (SS) Scale¹; agency of self-care measured by the Brazilian Portuguese version of the Appraisal of Self-Care Agency Scale – Revised (ASAS-R)^{6, 7}.

The WPI is one of the diagnostic variables of the 2010 ACR diagnostic criteria for FMS. It is a measure of the number of painful body regions (range 0 to 19) in the context of the past week.

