The VAS for pain was used to measure the pain intensity (range 0 to 10) at the moment of the examination. It is a continuous scale comprised of a 10-cm horizontal line, anchored by two verbal descriptors: no pain (score of 0) and worst imaginable pain (score of 10).

The SS Scale is another diagnostic variable of the 2010 ACR diagnostic criteria. It is a 4-component scale (range 0 to 12) composed of assessor-rated cognitive problems, unrefreshed sleep, fatigue and somatic symptom count. The timeframe for the assessment of the SS Scale is one week.

The ASAS-R is a multidimensional measure that evaluates the level of self-care agency regarding having, developing and lacking the power for self-care (range 15 to 75). It comprises 15 items responded in a five-point Likert scale ranging from 1 (totally disagree) to 5 (totally agree).

ProFibro app was programmed to register the date and time of each access to the app functions. Patients' adherence to the use of ProFibro app was assessed according to the number of accesses to the app functions after six weeks.

Interventions

A physical therapist researcher who was not involved in the outcome assessment opened the sealed envelopes and assigned participants to each group.

At their first individual session, the researcher gave the participants of the Experimental Group a smartphone with the ProFibro app installed, and the participants of the Control Group a paper book of similar content to that of the mobile app. The book was made after the development of the mobile app was completed.

Both groups received a 20-min introductory tutorial leading the participants through the main functions of the mobile app or book chapters. For further instructions, the information icon of the app functions and tutorial video in the menu were presented to the participants of the Experimental Group. Finally, the participants were instructed to explore and use the tools for six weeks with a view to self-care.

Statistical methods

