Primary and secondary outcomes were compared to baseline in each group and between groups. Change scores (the difference between the final and the baseline score) were used for comparison between groups. Analysis was performed on an intention-to-treat basis, with data carried forward from the baseline assessment in case of dropouts. Kolmogorov-Smirnov and Levene tests were used to verify normality and equality of variance of the data, respectively. Independent t tests were used with variables that were normally distributed, and Mann-Whitney rank sum tests were used with variables that were not normally distributed. A p-value <0.05 was considered statistically significant. These statistical tests were performed using software SigmaStat 3.5 (Systat Software, Inc, Erkrath, Germany).

In the analysis of clinical important changes, participants were classified as respondents if they scored higher than the MCID for an outcome, and non-respondents otherwise. The MCID for the FIQR total score was considered a change score of 8.1, and for VAS pain a change score of 2.^{2,8} For the other variables, no MCID was yet identified, and a change score of 15% was used.¹⁰

Funding

This work was supported by the Sao Paulo Research Foundation (FAPESP No. 2014/17547-5)

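### Within-arm comparisons with baseline cannot show that the app works on any outcome, and on the WPI and SS Scale they may also be inflated by regression to the mean if baseline scores were the qualifying scores

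*Combined protocol and SAP*

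**What the plan says.** Analysis (Statistical methods): "Primary and secondary outcomes were compared to baseline in each group and between groups". The only threshold given is "A p-value <0.05 was considered statistically significant". The section names the independent t test and the Mann-Whitney test, both two-sample methods, and gives no test for the comparison with baseline. Nothing marks the within-group results as descriptive. Between groups, change scores are compared, and dropouts have their baseline value carried forward.

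Entry (Participants): people are included if "diagnosed with FMS, according to the 2010 American College of Rheumatology (ACR) diagnostic criteria". After an emailed screening questionnaire, "potential participants were invited to a face-to-face assessment to confirm eligibility".

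Outcomes: the WPI and SS Scale are secondary outcomes, each covering one week. The section says of them "The WPI is one of the diagnostic variables of the 2010 ACR diagnostic criteria for FMS" and "The SS Scale is another diagnostic variable of the 2010 ACR diagnostic criteria". On timing it says "An outcome assessor blinded to the interventions enrolled participants in the trial and evaluated them at baseline and after six weeks of intervention".

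Comparator (Interventions): the researcher gave "the participants of the Control Group a paper book of similar content to that of the mobile app". There is no untreated arm.

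The Objectives section sets out to assess the app's effectiveness on quality of life, symptoms and self-care agency, and also to compare it with the book.

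**The concern.** A test against baseline takes zero change as its null hypothesis. In a trial where every participant receives self-care material, change over six weeks can come from the natural course of the condition, from taking part, from the shared content or from the app. One arm's change cannot separate these, whichever outcome is used and whichever paired test is chosen.

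On the WPI and SS Scale the null may itself be wrong. If people enter because they score high on an imperfectly repeatable one-week scale, and that same score is their baseline, part of the height is a bad week or measurement error. The mean is then expected to fall at six weeks with no effect.

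The stake is interpretive. Because the Objectives section has an effectiveness aim as well as a comparative one, a null app-versus-book result beside significant within-arm falls could be reported as showing that both tools work. The plan does not exclude that reading.

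**Working it through.** The plan gives no figure for the within-arm comparisons, so there is none to reproduce. The check asks how often a within-arm test would show improvement when nothing works.

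**Inputs from the documents**
- Threshold 0.05. Sidedness is not stated; two-sided is assumed, so 2.5% falls in the direction of improvement.
- 40 participants in total, after adding five to each group (Sample Size). Taken as 20 per arm; the allocation ratio is not stated.

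**Assumptions not in the documents**
- Baseline score equals qualifying score.
- Scores are normal and each scale is cut on its own.
- A fraction f of applicants is excluded by the cut, 10% to 40%.
- The six-week correlation before selection, r, is 0.5 to 0.8.
- No true change in either arm.
- A paired t-test is used, since the plan names no within-arm test.

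**Expected fall with no effect**

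Let z be the f quantile of the standard normal and λ = φ(z)/(1−f). The expected fall is (1−r)λ, in SD units of the unselected score.
- f=0.1, r=0.8: λ = 0.1755/0.9 = 0.195; fall = 0.2 × 0.195 = 0.039
- f=0.2, r=0.6: λ = 0.2800/0.8 = 0.350; fall = 0.4 × 0.350 = 0.140
- f=0.4, r=0.5: λ = 0.3863/0.6 = 0.644; fall = 0.5 × 0.644 = 0.322

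**Chance of a significant fall**

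The variance of the change is (1−r)²(1+zλ−λ²) + 1−r². In the middle case this is 0.16 × 0.583 + 0.64 = 0.733, so the SD is 0.856. The noncentrality is 0.140/0.856 × √20 = 0.731. A noncentral t with 19 degrees of freedom gives 10.3% beyond the critical value. Simulation (100,000 trials per setting) agrees:

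| Setting | App arm improves | App arm only | At least one arm | Between-arm test rejects |
|---|---|---|---|---|
| f=0.1, r=0.8 | 4.5% | 4.3% | 8.9% | 5% |
| f=0.2, r=0.6 | 10.3% | 9.2% | 19.4% | 5% |
| f=0.4, r=0.5 | 31.3% | 21.4% | 52.7% | 5% |
| Nominal | 2.5% | – | 5% | 5% |

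Repeat runs agree within about half a percentage point. With no selection (f=0) the app-arm figure returns to 2.4-2.6%.

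**Sensitivity of the app-arm figure**
- Baseline carried forward for 5 of 20 per arm: 4.1%, 8.2% and 23.3% in the three settings.
- Cut on the sum of the two scales rather than on each: about 4%, 8% and 23%.
- Only 5% excluded, r=0.8: 3.5%.
- Joint cut on both scales (assumed correlation 0.5 between them), r from 0.9 down to 0.6: 3% to 5% if 90% pass, 9% to 26% if 50% pass, 15% to 50% if 30% pass.
- Baseline measured afresh after eligibility: 2.5% if the entry score is equally correlated with both later scores, 3% to 7% if it correlates 0.1 more with baseline than with week six.

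**The case against.** The strongest reply is that the regression mechanism needs a fact the documents do not give. They describe a face-to-face visit to confirm eligibility and a baseline evaluation, but not that the qualifying WPI and SS scores served as baseline. One assessor who both enrols and takes baseline, with no later baseline described, makes reuse plausible and does not establish it. This stands, and so a reader who infers that false improvement on these scales is to be expected goes further than the text allows.

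The size also rests on assumptions. The criteria's cut-offs and combination rule are not given, and emailed pre-screening may have left few to fail at the visit. This stands too: the low end is close to nominal.

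Third, the p<0.05 sentence follows the two-sample tests, and no within-arm test is named. Applying the threshold to the comparisons with baseline is a reasonable reading, since it is the only threshold and nothing exempts them, but it is a reading.

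Fourth, the randomised comparison is already planned, and no sentence says that a within-arm p-value alone will support a claim of efficacy. That limits the harm. It does not remove it, because the effectiveness objective leaves room for such a claim.

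Finally, the lack of an untreated arm affects every outcome equally, so a remedy confined to two scales would not match the argument. This is accepted, and the fix covers all outcomes.

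**Conclusion.** The point holds in two parts of different strength.

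Unconditionally, within-arm change cannot be attributed to the app on any outcome, because both arms receive self-care material and there is no untreated arm.

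Conditionally, on the WPI and SS Scale, a null app arm may show significant improvement too often. If baseline scores were the qualifying scores, the rate on one scale is about 4% to 31% against 2.5%, for assumed exclusion of 10-40% and correlations of 0.5-0.8 with 20 per arm. With a fresh baseline the excess is small or absent. No regression to the mean of this kind is claimed for the FIQR, VAS or ASAS-R.

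A reader might infer that the app-versus-book comparison is biased as well. The calculation does not support that: the between-arm change-score test keeps its 5% level under this mechanism. Nor is it a general endorsement of that test; its power and its behaviour with carried-forward baselines under unequal dropout were not examined here.

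The change is worth making because it costs little and closes off a misleading reading. Confidence is medium, since the size depends on facts outside the documents.

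**What to change.** In Statistical methods:
- State that within-arm changes are descriptive for all outcomes, and at the least for the WPI and SS Scale. Report mean change with a 95% CI from paired differences, with no p-value and no claim of effect.
- Base every statement of effectiveness on the between-group comparison of change scores already planned.
- State whether the baseline WPI and SS scores were the ones that confirmed eligibility, and interpret changes on those scales accordingly. If they were, say that some fall in both arms may be regression to the mean.

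The cost is a few sentences, with no new data and no change to the between-arm analysis. The sponsor gives up the within-arm p-values.

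### The primary FIQR comparison uses raw change scores, and a normality test picks a mean or rank comparison; one pre-specified ANCOVA would fix the estimand and usually gain some precision

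*Combined protocol and SAP*

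**What the plan says.** All of the analysis rules are in the Statistical methods section of the combined protocol and SAP.

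- Between-group measure: "Change scores (the difference between the final and the baseline score) were used for comparison between groups".
- Assumption checks: "Kolmogorov-Smirnov and Levene tests were used to verify normality and equality of variance of the data, respectively".
- Choice of test: "Independent t tests were used with variables that were normally distributed", and "Mann-Whitney rank sum tests were used with variables that were not normally distributed".
- Missing data: "Analysis was performed on an intention-to-treat basis, with data carried forward from the baseline assessment in case of dropouts".

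The Outcomes section says that the assessor "evaluated them at baseline and after six weeks of intervention", so a baseline FIQR is available for every participant. The Sample Size section sets the dropout allowance: "Five participants were added to each group to compensate for possible dropouts, resulting in a total of 40 participants". That means 20 per group, of whom up to five may be lost.

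The documents name no model with baseline as a covariate, and no effect estimate or confidence interval for the group comparison. They do not say whether the normality check is run per group or pooled, or whether it is corrected for estimated mean and SD. They also do not say what follows if Levene's test fails.

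**The concern.** There are two linked problems, and the first is the more important.

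**The estimand is left to the data.** A t test concerns a difference in mean FIQR points. Mann-Whitney concerns rank ordering and gives no difference in mean FIQR points. A test run on the trial's own data decides which is reported. Under carry-forward the decision also depends on how many people drop out, because each dropout adds a tied zero to the change scores. Completers' scores could be exactly normal and the check could still fail.

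**Precision is left unused.** A change score adjusts for baseline with the slope fixed at 1. If the true slope is below 1, this over-corrects and adds variance. In a 40-person trial that loss matters.

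This is not a validity problem. The change-score contrast is unbiased over randomisations. Its sensitivity to chance baseline imbalance is the same thing as its extra variance and should not be counted a second time as bias.

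**Working it through.** **Inputs from the documents.** Difference 14 (given as 14%, read here as 14 points on the 0–100 FIQR total); SD 24.3; 20 per group; 5% significance (taken as two-sided); up to five dropouts per group; baseline carried forward.

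**Assumptions.** The documents do not give the baseline–final correlation r, so it is varied. Steps 2 and 3 read 24.3 as the SD of a single score and take baseline and final SDs as equal; both are relaxed later. The normality check is run at the 5% level.

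**1. The plan's own figure.** The number per group for 80% power is 2 × (1.960 + 0.842)² × 24.3² / 14² = 47.3, so 48 per group. The stated 30 participants in total does not reproduce. With SD 24.3 on the analysed variable, t-based power is 33% at 15 per group and 43% at 20. That is a separate issue, but it shows there is no spare precision.

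**2. Variances with equal SDs (s).**

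- Change score: 2(1 − r)s²
- ANCOVA: (1 − r²)s²
- Ratio of ANCOVA to change score: (1 + r)/2, which is below 1 for any r < 1
- Difference: (1 − r)²s², which is the variance from (1 − r) times the baseline imbalance

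The SD of the chance baseline difference is 24.3 × √(2/20) = 7.7 points.

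**3. Power without dropouts.** This uses the noncentral t distribution. For ANCOVA, df = 37 and the variance is inflated by 1 + 1/36 for the estimated slope. At r = 0.5:

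- Change score: SD = 24.3, noncentrality 14/7.68 = 1.82, df 38, power 43%.
- ANCOVA: SD = 24.3 × √0.75 = 21.04, noncentrality 14/(21.04 × √(37/36) × √0.1) = 2.07, power 52%.

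| r | Change-score t | ANCOVA |
|---|---|---|
| 0.3 | 32% | 45% |
| 0.5 | 43% | 52% |
| 0.7 | 63% | 69% |
| 0.8 | 80% | 83% |
| 0.9 | 98% | 98% |

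Simulated ANCOVA power agrees (45.1%, 52.5%, 69.0%, 83.0% at r = 0.3, 0.5, 0.7, 0.8).

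**4. If 24.3 is the SD of change.** The change-score test has 43% power. ANCOVA has 52% at r = 0.5 and 48% at r = 0.7. With five per group carried forward, the figures are 32% to 37% (r = 0.5) and 33% to 35% (r = 0.7).

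**5. Unequal SDs.** If the final SD is k times the baseline SD, the slope is rk and the variance difference is (1 − rk)²s², with s the baseline SD. The gain therefore vanishes as rk approaches 1.

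| k | r | Change-score t | ANCOVA |
|---|---|---|---|
| 0.9 | 0.7 | 67% | 78% |
| 1.1 | 0.7 | 58% | 61% |
| 1.1 | 0.8 | 75% | 75% |
| 1.25 | 0.7 | 50% | 50% |
| 1.25 | 0.8 | 66% | 65% |

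**6. How often the normality check switches to Mann-Whitney.** Simulation with normal completers, a 14-point effect and r = 0.5–0.7:

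| Dropouts per group | Corrected, per group | Corrected, pooled residuals |
|---|---|---|
| 0 | 10% | 5% |
| 1 | about 10% | about 5% |
| 2 | 15–16% | 7–8% |
| 3 | 26–27% | 13–15% |
| 5 | 68–69% | 38–45% |

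An uncorrected test switches in 0% of trials without dropouts and about 1% with five per group. Across all simulated trials, the t test and Mann-Whitney disagree on p < 0.05 in about 7% without dropouts and 9–11% with five per group.

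**7. Power with five per group carried forward (60,000 runs).**

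| r | Change-score t | Plan's rule, per-group check | Plan's rule, pooled check | ANCOVA |
|---|---|---|---|---|
| 0.5 | 32.2% | 29.2% | 32.9% | 37.0% |
| 0.7 | 48.5% | 44.5% | 48.8% | 52.0% |
| 0.8 | 65.1% | 60.4% | 65.0% | 66.9% |

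**8. Type I error, normal scores.** Plan's rule 4.7–5.5%; ANCOVA 4.9–5.0%.

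**9. Skewed scores.** With lognormal baseline and error and r = 0.7, the plan's rule is ahead: 95% against 78% without dropouts, and 73–74% against 68% with five per group. With milder (exponential) errors and no dropouts, the rule against ANCOVA is 51% against 55% at r = 0.5 and 76% against 71% at r = 0.7.

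**The case against.** The strongest reply is that a t test on change is valid and unbiased and has a clear estimand. Only the normality check leaves the estimand open, so dropping the check and keeping the change-score t test with its confidence interval would be enough. ANCOVA is then a matter of efficiency. This is correct, and it is why the recommendation rests mainly on the unfixed estimand.

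The size can also be challenged. Five dropouts per group is an allowance, not a forecast. At one per group the switch rate is no higher than with none, and it rises steeply only towards the full allowance. Most of the 9–11% disagreement is present without dropouts, so carry-forward adds only a few points. The ANCOVA gain depends on an SD ratio that the documents do not give, and it can vanish or slightly reverse if final scores are more spread out than baseline scores. Under strong skew the rank route wins by 17 points (95% − 78%), more than any ANCOVA gain shown here. All of this stands. It widens the range of likely benefit but does not give the plan a fixed primary estimand.

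Finally, WPI (0–19) and the SS Scale (0–12) are bounded and discrete, and the calculations cover only a continuous FIQR-like score. Using the same model for them is reasonable for consistency but was not tested.

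**Conclusion.** The concern holds and the change should be made. The plan does not commit to one estimate and confidence interval for its primary outcome. Whether it reports a mean or a rank comparison depends on an incompletely specified check which, with carry-forward, can respond to the number of dropouts. At five per group the switch rate runs from about 1% to 69% according to the version of the check, and that spread is itself evidence that the rule is under-specified.

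The efficiency gain is secondary and modest. For r of 0.5 to 0.8 with equal SDs and normal scores, ANCOVA adds about 10 to 3 power points without dropouts and about 5 to 2 with five per group carried forward, relative to the change-score t test. It is near nil at r = 0.9 or when the slope is close to 1, and negative under strong skew. These sizes rest on assumed r, on the SD ratio, and on reading 14% as 14 points. Validity and type I error are not in question.

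**What to change.** Name one primary analysis: a linear model of six-week FIQR total on group and baseline FIQR total, reporting the adjusted mean difference with its 95% confidence interval from the ordinary model-based standard error. If a robust standard error is wanted, specify a small-sample version with a t reference. With normal scores and five dropouts per group, simulated type I error was 6.7–7.2% for HC0 with a normal reference, 5.0–5.3% for HC1 with t(37), and 4.1–4.3% for HC3 with t(37).

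Remove the Kolmogorov-Smirnov step as a way of choosing the test, and keep Mann-Whitney on change scores as a named sensitivity analysis. Use the same model for WPI, VAS, SS and ASAS-R, noting that WPI and SS are bounded and discrete. The document is written in the past tense, so if results already exist, add this model to them and label it as not originally planned.

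The cost is a revised paragraph, a standard regression and one degree of freedom; no new data are needed. Some power may be lost against the rank test if scores are strongly skewed. The change does not repair the sample-size calculation or the carry-forward rule. With 25% dropout, carry-forward shrinks a 14-point effect to about 14 × 0.75 = 10.5 under either analysis.
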